- E 16. Patients who are treated with intranasal corticosteroid drops; intranasal steroid emitting devices/stents; nasal spray using exhalation delivery system, such as Xhance™, during screening period.
- E 17. Patients who are on INCS spray unless they have received stable dose for at least 4 weeks prior to Visit 1.
- E 18. Patients who have undergone sinus intranasal surgery (including polypectomy) within 6 months prior to Visit 1.
- E 19. For patients receiving systemic antifungals for AFRS treatment at screening: unwilling to stop antifungal therapy at screening.

E 20. Patients who have taken:

- Biologic therapy/systemic immunosuppressant to treat inflammatory disease or autoimmune disease (eg, rheumatoid arthritis, inflammatory bowel disease, primary biliary cirrhosis, systemic lupus erythematosus, multiple sclerosis, etc) within 4 weeks before Visit 1 or 5 half-lives, whichever is longer.
- Any investigational mAb within 5 half-lives or within 6 months before Visit 1 if the half-life is unknown.
- Anti-IgE therapy (omalizumab) within 4 months prior to Visit 1.

E 21. Treatment with a live (attenuated) vaccine within 4 weeks before the Screening Visit (Visit 1).

NOTE: For participants who have vaccination with live, attenuated vaccines planned during the course of the study (based on national vaccination schedule/local guidelines), it will be determined, after consultation with a physician, whether the administration of vaccine can be postponed until after the end of study (EOS), or preponed to before the start of the study without compromising the health of the participant:

- Patient for whom administration of live (attenuated) vaccine can be safely postponed will be eligible to enroll into the study.
- Patients who have their vaccination preponed can enroll in the study only after a gap of 4 weeks following administration of the vaccine.

E 22. Leukotriene antagonists/modifiers unless patient is on a continuous treatment for at least 30 days prior to Visit 1.

E 23. Initiation of allergen immunotherapy within 3 months prior to Visit 1 or a plan to begin therapy or change its dose during the screening or treatment period.

E 24. Patients received SCS during screening period.

E 25. Either intravenous immunoglobulin therapy and/or plasmapheresis within 30 days prior to Screening Visit (Visit 1).

Noncompliance to completion of the e-diary

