7 DISCONTINUATION OF STUDY INTERVENTION AND PARTICIPANT DISCONTINUATION/WITHDRAWAL

7.1 DISCONTINUATION OF STUDY INTERVENTION

7.1.1 Definitive discontinuation

In rare instances, it may be necessary for a participant to permanently discontinue (definitive discontinuation) study intervention. If study intervention is definitively discontinued, the participant will remain in the study to be evaluated for safety and efficacy. See the SoA ([Section 1.3](#)) for data to be collected at the time of discontinuation of study intervention and follow-up and for any further evaluations that need to be completed.

The Participants may withdraw from treatment with the IMP if they decide to do so, at any time and irrespective of the reason, or this may be the Investigator's decision. All efforts should be made to document the reasons for treatment discontinuation, and this should be documented in the eCRF.

Participants must be withdrawn from the study treatment (ie, from any further IMP) for the following reasons:

- At their own request or at the request of their legally authorized representative (legally authorized representative means an individual or judicial or other body authorized under applicable law to consent on behalf of a prospective participant to the participant's involvement in the procedure(s) involved in the research).
- If, in the Investigator's opinion, continuation in the study would be detrimental to the participant's well-being.
- At the specific request of the Sponsor.
- If they are treated with the specific prohibited medications mentioned in [Section 6.5.2](#).
- Sino-nasal surgery.
- If they miss 2 consecutive IMP doses.
- In the event of a protocol deviation, at the discretion of the Investigator or the Sponsor.
- Any code broken at the request of the Investigator.
- Pregnancy.
- Anaphylactic reactions or systemic allergic reactions that are related to IMP and require treatment (see [Section 10.9](#)).
- Diagnosis of a malignancy during study, excluding carcinoma in situ of the cervix, or squamous or basal cell carcinoma of the skin.
- Any opportunistic infection or other infections whose nature or course may suggest an immunocompromised status (see [Section 10.10](#)).

- Serum alanine aminotransferase (ALT) >3 upper limit of normal (ULN) and Total Bilirubin >2 ULN (see [Section 10.6](#)).
- Serum ALT >5 ULN if baseline ALT ≤ 2 ULN or ALT >8 ULN if baseline ALT >2 ULN (see [Section 10.6](#)).

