8.1.1.1 Lund Mackay score

Computerized tomography scans using the LMK scores allows the assessment of sinus opacification.

The CT scan LMK staging system represents the most widely established method of sinus CT scoring in clinical trials. Lund Mackay total score is based on assessment of the CT scan findings for each sinus area (maxillary, anterior ethmoid, posterior ethmoid, sphenoid, and frontal sinus on each side). The extent of mucosal opacification is rated on a 3-point scale ranging from 0 = normal to 2 = total opacification. In addition, the ostiomeatal complex is graded as 0 = not occluded, or 2 = occluded. The maximum score is therefore 12 per side for a maximum total score of 24, corresponding to the sum of all sinuses and the ostiomeatal unit. This scoring system has been validated in several studies (31, 32, 33).

Computed tomography scans should be performed anytime during the screening period before first administration of IMP at Visit 2 (baseline CT data), at Visit 5 (Week 24), and Visit 7 (Week 52). Whenever possible, a cone beam CT scan should be utilized. In countries for which a specific approval procedure for the CT scan is required by a different committee than the local Independent Ethics Committee (IEC)/Institutional Review Board (IRB), these countries will be exempted from all the planned study CT scans until approval from these committees is received. A 3-month window is required between 2 CT scans in screening period if a participant needs to be rescreened. If Participant who discontinue the study intervention prematurely, the CT scan will be performed as soon as possible, with all other assessments normally planned in EOT Visit (Visit 7). Week 24 CT scan is not required for adolescents/children. In any case, participants may not have more than 3 CT scans during the study. If a participant needs to have CT scan around the time of surgery the next scheduled CT scan per protocol does not need to occur after surgery for AFRS.

The CT scan will be performed locally and centrally reviewed in a pre-specified manner as described in the Image Acquisition Standards (IAS) and Image Interpretation Standards (IIS) and the SoA (Section 1.3).

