3.2.2 Main analytical approach

The primary endpoint will be analyzed with the estimand defined according to the following attributes:

- Endpoint: Change from baseline in LMK score at Week 52
- Treatment condition: dupilumab will be compared to placebo
- Analysis population: ITT population
- Intercurrent events (IE):
 - The following intercurrent events will be handled with a composite strategy; data after the IE will be excluded and the worst post-baseline value on or before the start of the IE will be assigned to the Week 52 value (WOCF); for participants with no post-baseline values, the baseline value will be used.
 - Undergo/plan to undergo surgery for AFRS prior to Week 52
 - Taking SCS for any reason prior to Week 52

- The following IEs will be handled with the treatment policy strategy (without IEs that need to be handled with composite strategy). All assessments after starting such IE will be included.
 - Discontinuing the study intervention
 - Taking antifungals or other prohibited/rescue medications
- Population-level summary:

The primary endpoint will be analyzed using an analysis of covariance (ANCOVA) model with the baseline LMK score, intervention group, time from last surgery (≤ 2 years, >2 years), and region (Americas: Argentina, USA, Canada; Asia: China, Japan, India, Turkey, Saudi Arabia) as covariates, with intercurrent event strategies and missing data handling as defined in [Table 3](#).

Data of participants who undergo/plan to undergo surgery for AFRS or take SCS for any reason on or before Week 52 will be excluded from analysis after the IE, and the worst postbaseline value on or before the start of IE will be used to assign missing endpoint value (for participants whose postbaseline values are all missing, the baseline will be used to impute). Participants who discontinue the intervention prematurely are encouraged to follow the planned clinical visits and in those participants who did not have any of the above IE, all data collected after intervention discontinuation will be used in the analysis. For these participants, missing data may still happen despite all efforts to collect the data after treatment discontinuation. A multiple imputation (MI) approach will be used to impute missing endpoint value, and this MI method will use all participants excluding participants with the above IE. The imputation number will be 40.

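### The LMK estimand counts steroids for any reason as failure but surgery only when it is for AFRS, so a scan cleared by a differently labelled sinus operation can be used as a response

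*SAP*

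**What the plan says.** SAP 3.2.2 lists two composite events for the primary endpoint: "Undergo/plan to undergo surgery for AFRS prior to Week 52" and "Taking SCS for any reason prior to Week 52". After either one, later data are dropped and the worst post-baseline value up to the event is carried to Week 52, or the baseline value if there is none. SAP Table 2 has the same pair. Protocol Table 7 has it too, along with prohibited biologics, which the SAP has since removed.

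"Discontinuing the study intervention" is handled by treatment policy: "All assessments after starting such IE will be included", provided no composite event has occurred. For imputation, "this MI method will use all participants excluding participants with the above IE". The continuous secondary endpoints follow the same scheme.

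Three other places bear on the point:

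- Protocol 7.1.1 lists "Sino-nasal surgery" among the reasons for withdrawing IMP, with no indication attached.
- Protocol 8.1.1.1 relaxes the CT schedule only for AFRS operations: "the next scheduled CT scan per protocol does not need to occur after surgery for AFRS". It also caps CT scans at three per participant.
- SAP Table 7 assigns any CT after Day 266 to Week 52, with no upper limit, and any earlier post-baseline CT to Week 24.

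No event list names sino-nasal surgery for another reason, and no adjudication of the surgical indication is described.

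**The concern.** The LMK score measures opacification, and sinus surgery removes it mechanically. The reason written on the form does not change that. The plan accepts this reasoning for steroids, where indication is ignored, but makes surgery depend on an investigator's label. The entry criteria also ignore indication: E18 excludes "Patients who have undergone sinus intranasal surgery (including polypectomy) within 6 months prior to Visit 1".

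If an operation is recorded under another indication and no SCS is given, the surgical result can be credited to the allocated arm as observed response. On placebo this shrinks the treatment difference; on dupilumab it enlarges it. The same gap affects the continuous endpoints that surgery alters directly: LMK at Week 24, nasal polyp score (NPS) and 3D CT volume.

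**Working it through.** **The plan's own figure.** SAP 3.9 gives power above 99% for the primary endpoint with 62 participants (31 per arm) at two-sided 0.05. The assumed effect and SD are not in the available text, so this cannot be reproduced, and the point does not depend on it. Working backwards, 99% power needs a standardized difference of at least (1.960 + 2.326) × √(2/31) = 1.09, which is 5.44 LMK points at an assumed SD of 5.

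**Tracing one participant.** Suppose a sino-nasal operation is recorded under a non-AFRS indication, with no SCS.

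1. Neither composite event is met, so worst-observation carried forward does not apply.
2. Protocol 7.1.1, as written, stops IMP. The only listed event that then fits is discontinuation, so later data are kept. If 7.1.1 was meant to cover only AFRS surgery, no intercurrent event applies and the data are still used as observed.
3. The CT relaxation does not apply, so a later scheduled scan is still expected, within the cap of three.
4. If a post-operative CT falls after Day 266, it can be the Week 52 value. This can happen when an adult has the Week 24 scan and is operated on late in the treatment period. It can also happen in an adolescent or child, for whom no Week 24 scan is required and a third scan remains available.
5. If an adult has the Week 24 scan and then a discontinuation scan by Day 266, the cap leaves no Week 52 scan and the value is imputed. If the scan selected for the Week 24 window is post-operative, the clearance enters as an imputation predictor.
6. The participant carries wocffl = N, stays in the imputation set, and so also informs other participants' imputed values.

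**Size per case.** Let g be the gap between the value that would have been carried forward and the post-operative score. The shift in the arm mean, before covariate adjustment, is g/31. All values of g are assumptions.

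| g (LMK points) | Shift in arm mean |
|---|---|
| 8 | 8/31 = 0.26 |
| 14 (for example 18 to 4) | 14/31 = 0.45 |
| 18 | 18/31 = 0.58 |
| 24 (full scale) | 24/31 = 0.77 |

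**Effect on power.** Assume exactly 99% power to begin with, SD 5, variance unchanged and all cases on placebo. One case with g from 6 to 18 leaves 98.5% to 96.9%. Three cases leave 96.9% to 83.0%; for g = 18 the difference falls from 5.44 to 5.44 − 3 × 18/31 = 3.70 points.

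**The case against.** The case against is substantial on frequency.

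- Every participant must have AFRS with polyps confirmed by endoscopy. The protocol's study rationale includes polypectomy in AFRS treatment, and its background section describes visual, facial and bony complications as consequences of AFRS. Operations for polyps or for such complications should therefore be recorded as AFRS surgery.
- E01 excludes septal deviation that occludes a nostril and antrochoanal polyps, E02 excludes nasal tumours, and E13 excludes planned major surgery. Few other indications remain.
- The protocol describes an oral steroid taper after sinus surgery as the usual practice. Any such use triggers the SCS event whatever the surgical label.
- E18 concerns history before entry, so it is weak evidence about on-study failure. The bare wording in 7.1.1 could be shorthand for the AFRS surgery described in protocol 6.5.3 and 8.1.2.

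All of this stands, and it makes the problem uncommon. It does not close the gap, because the event definition would then rely on a second treatment, SCS, to catch the first.

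A reader might go further and infer that the SAP assigns such surgery to treatment policy and always scores it as improvement. The documents do not support that. The surgery is unlisted, treatment policy is reached only by inference, and scan timing, the three-scan cap and SCS use often prevent a post-operative Week 52 value. Nor do they support inferring a bias towards dupilumab: the direction depends on the arm, and if such operations are commoner on placebo the error is conservative.

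**Conclusion.** The asymmetry is real, and the stated rules leave a path for a surgically cleared scan to serve as the Week 52 LMK value. That path needs a sino-nasal operation, a non-AFRS label, no SCS and a usable post-operative scan. The documents give no rate for this combination; it is probably rare. Each case moves an arm mean by about 0.26 to 0.58 LMK points under assumed drops of 8 to 18 points. Against an effect large enough for the stated power, one case would matter little; several in one arm could matter.

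This is a cheap improvement to the estimand and does not undermine the primary analysis. A reader might also infer that the rescue endpoint is misdefined. That does not follow: its objective is the need for rescue treatment, and restricting its surgical component to AFRS surgery is a defensible choice. One operation changes an arm's proportion by 1/31 = 3.2 percentage points, which a sensitivity analysis can show.

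**What to change.** The changes are to the analysis only and should be made before unblinding:

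- In SAP Table 2 and 3.2.2, define the composite surgical event as any actual or planned sino-nasal surgery, including polypectomy, regardless of recorded indication. Apply this to the primary endpoint and to LMK at Week 24, NPS and 3D CT. Bring protocol Table 7 into line.
- Set wocffl and the imputation exclusion to the same definition.
- Leave the rescue endpoint as surgery for AFRS. Add a listing of all sino-nasal operations by recorded reason and a sensitivity analysis that counts all of them.
- Reconcile the wording of protocol 7.1.1, the CT provision in 8.1.1.1 and the intercurrent-event lists, which now describe surgery differently.

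The cost is SAP wording, one flag derivation, one listing and one sensitivity analysis. SAP Appendix 3 already codes concomitant procedures, which should help to identify the operations. The downside is that an occasional operation unrelated to AFRS is scored as failure, a price the plan already accepts for SCS.

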4 STUDY DESIGN

4.1 OVERALL DESIGN

This is a Phase 3, multicenter, 52-week treatment, parallel-group, double-blind, randomized, placebo-controlled study to investigate the efficacy of dupilumab 300 mg q2w for adults and adolescents/children (≥ 6 to < 12 years) ≥ 60 kg, or dupilumab 200 mg q2w for adolescents/children ≥ 30 kg and < 60 kg, dupilumab 300 mg q4w for adolescents/children ≥ 15 kg and < 30 kg with signs and symptoms of AFRS. The study will primarily investigate the efficacy of dupilumab to reduce disease burden in the sinuses (sinus opacification) by radiographic imaging. In addition, the study will also evaluate efficacy of dupilumab to reduce the need for repeated SCS and/or surgery, nasal polyps burden, clinical symptoms, and explore other measures of disease activity.

Approximately 62 participants (31 per arm) with AFRS who satisfy the inclusion and exclusion criteria will be randomized in a 1:1 ratio to receive either dupilumab or matching placebo:

- Dupilumab 300 mg q2w for all adults, 300 mg q2w for adolescents/children ≥ 60 kg at screening, or 200 mg q2w for adolescents/children ≥ 30 kg and < 60 kg at screening, or 300 mg q4w for adolescents/children ≥ 15 kg and < 30 kg at screening.
- Matched placebo.

Randomization will be stratified first by age (adults versus adolescents/children [≥ 6 years old]). In adults, randomization will be stratified further by time from last surgery (≤ 2 years [including surgery naive participants], > 2 years), disease pattern (unilateral/bilateral in the endoscopy at screening), and country. In adolescents/children, randomization will not be stratified further.

Duration of study period (per participant):

- Screening period (2 to 4 weeks): to determine a participant's eligibility and continue with his/her own background intranasal corticosteroids (INCS) prior to randomization.
- Randomized IMP intervention period (52 weeks ± 3 days): to randomize the participants into a treatment arm and treat with dupilumab or placebo dose regimen.
- Follow-up period (12 weeks ± 5 days): to continue to collect data for PK, immunogenicity, safety, and efficacy after the participant has completed the randomized IMP intervention period.

The total duration of study participation for participants that complete the randomized treatment period and posttreatment follow-up is approximately 68 weeks. The schedule of the visits is described in the specific flow-chart in [Section 1.3](#).

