6.3 MEASURES TO MINIMIZE BIAS: RANDOMIZATION AND BLINDING

The randomized intervention kit number list is generated centrally by Sanofi and IMPs are packaged in accordance with this list. The randomization and intervention allocation are performed centrally by an IRT. The IRT generates the participant randomization list and allocates the intervention number and the corresponding intervention kits to the participants according to it. Before the study is initiated, the telephone number and call-in directions for the interactive voice response system and/or the log in information and directions for the interactive web response system will be provided to each site.

Participants will be randomized in a 1:1 ratio treatment arm described in [Table 2](#).

The randomization will be stratified by age (adults versus adolescents/children) first. In adults, randomization will be further stratified by time from last surgery (≤ 2 years, > 2 years), disease pattern (unilateral/bilateral in the endoscopy at screening), and country. In adolescents/children, randomization will not be further stratified.

At screening (Visit 1), the Investigator or designee will contact the IRT system to receive the participant number. If a participant who had previously failed screening is approached for rescreening, a new ICF/assent form must be signed. In such case, a new participant number will be assigned by IRT.

A randomized participant is defined as a participant who has been allocated to a randomized intervention regardless whether the treatment was administered or not (ie, participant registered by the IRT). A participant cannot be randomized more than once in the study.

Study intervention will be dispensed at the study visits summarized in Schedule of Activities (SOA) (see [Section 1.3](#)). Returned study intervention should not be re-dispensed to the participants.

Methods of blinding

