9.4.2 Primary endpoint(s)

The primary estimand for the primary endpoint of change from baseline in LMK score at Week 52 is the composite/treatment policy strategy, as described in [Table 7](#).

Table 7 - Summary of primary estimand for the primary endpoint

Endpoint Category	Estimands			
	Endpoints	Population	Intercurrent event(s) handling strategy and missing data handling	Population-level summary
Objective: To evaluate the efficacy of treatment with dupilumab to reduce sinus opacification in a population with allergic fungal rhinosinusitis (AFRS)				
Primary endpoint	Change from baseline in LMK score at Week 52	ITT	
The following intercurrent events will be handled with a composite strategy; data after the IE will be excluded and the worst post-baseline value on or before the start of the IE will be assigned to the Week 52 value (WOCF); for participants with no post-baseline values, the baseline value will be used.
 
 Undergo/plan to undergo surgery for AFRS prior to Week 52 Taking SCS for any reason prior to Week 52 Starting prohibited biologics prior to Week 52 
The following IEs will be handled with the treatment policy strategy (without IEs that need to be handled with composite strategy). All assessments after starting such IE will be included.
 
 Discontinuing the study intervention Taking antifungals or other prohibited/rescue medications 
In addition, the missing data imputation rules are as follows:
 
 For missing data, a multiple imputation approach will be used to impute missing Week 52 values, and this multiple imputation will use all data from participants excluding participants who undergo/plan to undergo surgery for AFRS on or before Week 52. 	ANCOVA model with intervention group, time from last surgery (≤ 2 years, > 2 years), region (countries combined), and relevant baseline measurement as covariates is used. Statistical inference obtained from all imputed data by ANCOVA model will be combined using Rubin's rule.

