1 INTRODUCTION

1.1 STUDY DESIGN

This is a Phase 3, multicenter, 52-week treatment, parallel-group, double-blind, randomized, placebo-controlled study to investigate the efficacy of dupilumab in adults and pediatrics aged 6 years and older with signs and symptoms of AFRS.

After a screening phase of 2 to 4 weeks, approximately 62 participants with AFRS who satisfy the inclusion and exclusion criteria will be centrally randomized (using permuted block randomization schedule) via Interactive Response Technology (IRT) in a 1:1 ratio to receive either dupilumab or matching placebo. Randomization will be stratified first by age (adults versus adolescents/children [≥ 6 years old]). In adults, randomization will be stratified further by time from last surgery (≤ 2 years [including surgery naive participants], > 2 years), disease pattern (unilateral/bilateral in the endoscopy at screening), and country. In adolescents/children, randomization will not be stratified further.

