Each of the imputed complete data will be analyzed by fitting an ANCOVA model as described above. Statistical inference obtained from all imputed data will be combined using Rubin's rule. Descriptive statistics including number of participants, mean, standard error, and least squares (LS) mean changes (and standard error) will be provided. In addition, difference of the dupilumab group against placebo in LS means and the corresponding 95% confidence intervals (CI) will be provided along with the p-value.

A separate summary of primary endpoint will be provided for pediatric patients.

The multiple imputation and analysis model for the primary analysis of change from baseline in LMK values will be built with the following sample SAS code.

1. 40 datasets with a monotone missing pattern will be obtained, induced by Markov Chain Monte Carlo (MCMC) method on all participants excluding participants who undergo/plan to undergo surgery for AFRS or take SCS for any reason on or before Week 52.

```
proc mi data=ads out=monotone n impute=40 seed=16724;
  where wocfl='N';
  var time region trt01p value0 value24 value52;
  mcmc chain=multiple impute=monotone;
run;
```

2. For each of the imputed datasets with monotone missing pattern in step 1, the remaining missing data at baseline and post-baseline visits will be imputed using regression method for the monotone missing pattern with adjustment for covariates including time from last surgery (≤ 2 years, > 2 years), region (Americas, Asia) and intervention group.

```
proc mi data=monotone out=dat_mi nimpute=1 seed=16724 minimum=... 0 0 0  
maximum=... 24 24 24; /*LMK score range is 0-24*/
```

```
    by _imputation_;  
    class time region trt01p;  
    var time region trt01p value0 value24 value52;  
    monotone reg (/details);  
run;
```

3. Each of the 40 imputed datasets will be merged with one dataset imputed by WOCF approach, and then be analyzed using the main statistical model. These 40 imputed datasets will be saved.

```
%macro w1;  
    %do i=1%to 40;  
        data wocf&i.;  
        set ads;  
        where wocffl='Y';  
        _imputation_=&i.;  
        run;  
    %end;  
    data wocf_all;  
        set %do j=1 %to 40; wocf&j. %end;;  
        run;  
    %mend w1;  
  
%w1;  
  
data mi;  
    set dat_mi wocf_all;  
run;  
  
proc sort data=mi; by _imputation_; run;  
  
proc glm data=mi;  
    by _imputation_;  
    class time region trt01p;  
    model change=time region trt01p value0;  

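### The primary Week 52 LMK ANCOVA omits age group, the first randomisation stratum, without a stated reason; adding it would be a small, low-cost gain in precision

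*SAP*

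**What the plan says.** Both documents put age first in the randomisation. SAP 1.1: "Randomization will be stratified first by age". Protocol 4.1: "Randomization will be stratified first by age (adults versus adolescents/children". Protocol 6.3: "The randomization will be stratified by age (adults versus adolescents/children) first". Only adults are stratified further, by time from last surgery, disease pattern and country.

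The primary model in SAP 3.2.2 is an "analysis of covariance (ANCOVA) model with the baseline LMK score, intervention group, time from last surgery" and region. The sample code agrees: "model change=time region trt01p value0". The imputation code uses "var time region trt01p value0 value24 value52". Neither contains age. Protocol 9.4.2, Table 7, has the same covariates: "ANCOVA model with intervention group, time from last surgery", with region and the baseline measurement.

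Age at or near the randomisation cut appears elsewhere, but not as an adjustment. SAP 3.2.2 adds: "A separate summary of primary endpoint will be provided for pediatric patients". SAP 3.7.1.1 splits pharmacokinetic results at 18 years. The age subgroup for the primary endpoint in SAP 3.7.2 is cut at 40 years, which is not the randomisation cut.

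**The concern.** A factor used to stratify randomisation is normally carried into the primary model. If it is prognostic, stratification removes its contribution to the real variability of the treatment difference. A model that omits it leaves that contribution in the residual, so the reported standard error is larger than it need be and the test is slightly conservative.

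The plan explains the absence of another stratum. SAP 3.9 says disease pattern left the model because unilateral participants were rare. Age, the first-level stratum, gets no such sentence, so a reader cannot tell whether it was left out on purpose. What is at stake is a little precision and a clear rationale, not the validity of the result.

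**Working it through.** **The plan's own figure.** SAP 3.9 states power above 99% for the primary endpoint. The public text gives no effect size or SD, so this cannot be reproduced. With 31 per arm and two-sided alpha 0.05, the normal approximation shows what it implies: (1.960 + 2.326) × √(2/31) = 1.09 residual SDs.

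**Degrees of freedom.** The current model has five parameters (intercept, treatment, baseline, time, region): 62 − 5 = 57 with complete data. Adding age gives 56. The critical value goes from 2.00247 to 2.00324 (+0.04%).

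**Gain if age is prognostic.** The documents give no paediatric count, SD or age effect, so all of these are assumed: n = 62, near 1:1 within age group, residual SD 5, k under-18s, and an age difference of d points after baseline adjustment. Mean model standard errors over 6,000 simulated trials, without / with age:

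| k | d = 0 | d = 2 | d = 4 |
|---|---|---|---|
| 3 | 1.2967 / 1.3006 | 1.3016 / 1.3007 (+0.07%) | 1.3188 / 1.3026 (+1.24%) |
| 5 | 1.2965 / 1.2990 | 1.3047 / 1.2992 (+0.42%) | 1.3311 / 1.3017 (+2.26%) |
| 6 | 1.2969 / 1.2974 | 1.3048 / 1.2960 (+0.68%) | 1.3310 / 1.2954 (+2.75%) |
| 12 | 1.2963 / 1.2968 | 1.3164 / 1.2999 (+1.27%) | 1.3620 / 1.2979 (+4.94%) |

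Percentages show how much larger the standard error is without age. As a check, √(1 + f(1−f)d²/25) − 1 with f = k/62 gives 0.59% for k = 5, d = 2 and 4.88% for k = 12, d = 4. A separate simulation at k = 12 and an age effect of one residual SD gave 0.2755 / 0.2560, or +7.6%.

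**Validity.** Type I error of the current model was 3.9% to 5.4% in the first simulation and 3.7% to 5.3% in the second (Monte Carlo SE 0.3 points). Neither model showed bias. At k = 12 and one SD, the actual spread of the estimate was 0.2578 without age and 0.2574 with it. The omission therefore overstates the reported standard error and hardly changes the estimate's real variability.

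**Power.** If power were exactly 99% with age in the model, standard errors larger by 0.42% to 4.94% would give 98.95% to 98.32%. In the second simulation the largest loss was 0.8 points (98.2% to 97.4%).

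**Cost if age is not prognostic.** From the d = 0 column, adding age raises the standard error by about 0.2% at k = 5 and 0.04% at k = 6 and 12. This assumes near balance within age. The SAP specifies permuted blocks, but the public text gives no block size. With imbalance the inflation is 1/√(1 − r²), where r is the age–treatment correlation (31 per arm):

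- 4:2 at k = 6: r² = (1/62)² / [0.25 × (6/62)(56/62)] = 0.0119, so +0.60%. With assumed blocks of 4 this happens when the fifth and sixth under-18s share an arm, probability 1/3.
- 5:2 at k = 7: r² = (1.5/62)² / [0.25 × (7/62)(55/62)] = 0.0234, so +1.2%. Fixed blocks of 4, 6 or 8 cannot produce this split; mixed or larger blocks can.
- 4:1 at k = 5: r² = (1.5/62)² / [0.25 × (5/62)(57/62)] = 0.0316, so +1.6%. This is possible with blocks of 8.

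**Imputation.** Assumed: 40 imputations, 10% missing Week 52 values, no under-18 Week 24 scans, 400 runs. Mean combined standard errors for no age / age in the ANCOVA only / age in the ANCOVA and the Week 52 imputation step: 1.3860 / 1.3576 / 1.3502 (k = 6, d = 4); 1.4316 / 1.3840 / 1.3717 (k = 12, d = 4); 1.3523 / 1.3530 / 1.3528 (k = 6, d = 0). Mean estimates differed by at most 0.02.

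**The case against.** The strongest reply is that little follows from this. The pre-specified test is valid and matches the protocol, and power has room to spare. The benefit rests on assumed inputs: the 4.9% figure needs 12 under-18s of 62 and a 4-point age effect left after baseline LMK. The documents suggest few under-18s. Protocol 2.2 puts mean age in the 20s to 30s and describes cases at 6 to 12 years as rare, and SAP 3.7.1.1 provides for one or no evaluable under-18 in the dupilumab arm. Protocol 4.2 calls the disease in children similar to that in adults, although the same sentence reports unilateral polyposis in 50% of children and about 30% of adults. All of this stands, and it keeps the point minor.

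It is also fair that chance imbalance in a small stratum can cost as much as the low-end gain. A threshold of 5 makes the model depend on a count, and SAP 3.7.2 uses that number permissively, for subgroup categories only. Fixing the rule on blinded counts meets the first part of that complaint; the number itself remains borrowed. The rarity given as the reason for dropping disease pattern might apply to under-18s too, but the public text does not say so. Not all sections are public, so a rationale elsewhere cannot be excluded.

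A reader might infer that SAP 3.1 contradicts 3.2.2, because it names age among the stratification factors used in analyses. That sentence only gives data sources. It also names disease pattern, which is not in the model either, so it promises no adjustment.

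**Conclusion.** The point holds as a low-severity matter of efficiency and transparency. Age group is the first stratum, it is absent from the primary ANCOVA and the imputation, and no reason is stated in the public text.

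Two stronger conclusions are tempting and unsupported. The SAP has not departed from the protocol, since the two models agree. Nor is the analysis biased, anti-conservative or underpowered.

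The size depends on assumptions about the paediatric count, the residual SD and the age effect. With at least 5 under-18s, the reported standard error is about 0.4% to 5% larger than necessary if age is prognostic after baseline adjustment, and up to about 8% larger at one residual SD. If age is not prognostic there is no gain, and adding it carries the small cost shown above.

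**What to change.** Before unblinding:

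1. Add age group (adult versus under 18) to CLASS and MODEL in the primary `PROC GLM`, and to the ANCOVA for continuous secondary endpoints measured in both age groups.
2. Fix a rule now, applied to blinded counts: with fewer than 5 under-18s in the analysis, keep the current model. Say that the number is borrowed from SAP 3.7.2.
3. In the second `PROC MI`, enter age in the `value52` regression only, for example `reg(value24 = time region trt01p value0) reg(value52 = time region trt01p agegrp value0 value24)`. Add `agegrp` to CLASS and VAR, and extend the positional minimum and maximum lists so that the 0–24 bounds still fall on the LMK variables. Leave age out of the `value24` step. Protocol 8.1.1.1 does not require the Week 24 scan in under-18s, so few or none will have one; an early-discontinuation scan up to Day 266 could still count as Week 24 under SAP Table 7.

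If the sponsor prefers the current model, one sentence giving the reason is enough. After unblinding, that sentence plus a labelled sensitivity analysis with age would be the appropriate course.

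The cost is a short SAP edit, the code changes above and 1 of 57 degrees of freedom. No new data are needed and the sample size does not change. Re-stratifying the Mantel-Haenszel analysis by age and an adults-only Week 24 LMK analysis are optional extras on which this point does not depend.
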